##### 3.1.1 *Pharmacokinetic and PK-PD Modeling*

- Serum trough levels ( $C_{min}$ ) of Ziltivekimab will be measured at all visits. On dosing Week 1, 5, 9, 13, 17, and 21, trough PK samples to be collected within approximately -0.5 h pre-dose. Single PK blood samples will also be collected on Weeks 2, 4, 7, 23, 24/ET, 28, and 32/ET around the same time as the pre-dose samples were collected on previous dosing visits.
- The total IL-6 AUC will be described.
- The relationship between trough Ziltivekimab levels and primary pharmacodynamic endpoints, specifically total plasma IL-6 and hs-CRP, will be described.

### **3.1.2 Safety Endpoints**

- Proportion of patients with AEs, SAEs, severe hematologic AEs, severe non-hematologic AEs, and AEs leading to discontinuation.
- Proportion of subjects with thrombolysis in myocardial infarction (TIMI) major bleeding event.
- Description and frequency of events of special interest by treatment group:
  - Serious infections.
  - Severe injection-related reactions.
  - Gastrointestinal perforations.
  - Hypersensitivity reaction during study drug administration.
  - Anaphylaxis occurring at any time, even if considered unrelated to the study drug. A CRF for the collection of the details of such reactions will be available in the electronic data capture (EDC) system.
  - Neutrophil  $<500/\text{mm}^3$  (severe) or neutrophil  $<1000/\text{mm}^3$  (severe) with evidence of concurrent infection. These events will be separately summarized by treatment group and dose.
  - Thrombocytopenia (platelet count  $<50,000/\text{mm}^3$  [severe]) or platelet count  $<75,000/\text{mm}^3$  (moderate) with evidence of concurrent TIMI major bleeding. These events will be separately summarized by treatment group and dose.
  - Malignancies

- Description of additional safety assessments by treatment group and dose: vital signs, electrocardiogram (ECG), clinical laboratory, and anti-drug antibodies (binding and neutralizing).

### **3.1.3 Pharmacodynamic Endpoints**

#### **3.1.3.1 Primary**

- Difference in percent change in hs-CRP levels from Baseline (average of the hs-CRP value prior to randomization and Day 1) to Week 13 between each active group and placebo.

#### **3.1.3.2 Secondary**

All secondary and exploratory analyses will be performed with the Intent-to-Treat (ITT) population.

- Difference in change in SAA from Baseline to Week 13 between each active group and placebo.
- Difference in percent change in fibrinogen from Baseline to Week 13 between each active group and placebo.

### 3.1.3.3 Exploratory

- Difference in percent change in hs-CRP levels from Baseline to End of Treatment (Weeks 23 through 24) between each active group and placebo.
- Difference in percent change in serum NT-pro-BNP from Baseline (average of the NT-pro-BNP value prior to randomization and Day 1) to Week 13 and to End of Treatment (Weeks 23 through 24) between each active group and placebo.
- Difference in change in SAA from Baseline to End of Treatment (Weeks 23 through 24) between each active group and placebo.
- Difference in percent change in fibrinogen from Baseline to End of Treatment (Week 24) between each active group and placebo.
- Difference in change in hemoglobin from Baseline (average of the two most recent hemoglobin values prior to randomization and Day 1) to Week 13 and to End of Treatment (Weeks 23 through 24) between each active group and placebo.
- Difference in change in serum albumin from Baseline (average of the two most recent serum albumin values prior to randomization and Day 1) to Week 13 and to End of Treatment (Weeks 23 through 24) between each active group and placebo.
- Proportion of patients achieving hs-CRP response at Week 13 and to End of Treatment (Weeks 23 through 24), defined as hs-CRP <2.0 mg/L in each active group and placebo.
- Difference in change in ST2 from Baseline to Week 13 and to End of Treatment (Week 24) between each active group and placebo.
- Difference in percent change in Lp(a) from Baseline to Week 13 and to End of Treatment (Weeks 23 through 24) between each active group and placebo.
- Difference in percent change in LDL-C, triglycerides, ApoB, ApoA1, ApoB/ApoA1, and lipid profile by NMR spectroscopy from Baseline to Week 13 and to End of Treatment (Weeks 23 through 24) between each active group and placebo.
- Difference in change of creatinine based eGFR and cystatin C-based eGFR from Baseline to Week 13 and to the End of Treatment (Weeks 23 through 24) between each active group and placebo.

- Difference in change of UACR from Baseline to Week 13 and to End of Treatment (Weeks 23 through 24) between each active group and placebo.
- Difference in change of the total fatigue score (PROMIS Fatigue 13a short form and selected items from the PROMIS Fatigue item bank) from Baseline to Week 13 and to End of Treatment (Weeks 23 through 24) between each active group and placebo.
- Difference in change of the PROMIS interest in sexual activity item from Baseline to Week 13 and to End of Treatment (Week 24) between each active group and placebo.
- Difference in change of the Corvidia ePRO items from Baseline to Week 12 and to End of Treatment (Weeks 23 through 24) between each active group and placebo.
- Difference in change of the PGIS index from Baseline to Week 12 and to End of Treatment (Week 24) between each active group and placebo.
- Descriptive analyses of the PGIC index at Weeks 5, 13 and End of Treatment (Week 24) in each active group and placebo.
- Difference in change of the Optum SF-36 v2® Health Survey physical component summary (PCS), mental component summary (MCS) and domain scores from baseline to Week 13 and to End of Treatment (Weeks 23 through 24) between each active group and placebo.
- Difference in change of the EQ-5D-5L index from Baseline to Week 12 and to End of Treatment (Week 24) between each active group and placebo.
- Evaluation of the psychometric properties of the PROMIS Fatigue 13a short form and selected items from the PROMIS Fatigue item bank and the Corvidia ePRO items in CKD patients – to be described in a PRO psychometric analysis plan.
- Descriptive analyses by dose and treatment may be conducted on samples stored for analysis of exploratory biomarkers, genomic and transcriptomic analysis.
- Difference in change in TSAT from Baseline to peak level, Week 13 and End of Treatment (Weeks 23 through 24), between each active group and placebo.
- Difference in change in CHr from Baseline to peak level, Week 13 and to End of Treatment (Week 24) between each active group and placebo.
- Difference in change in TIBC from Baseline to Week 13 and to End of Treatment (Weeks 23 through 24) between each active group and placebo.
- Difference in change in serum ferritin from Baseline to Week 13 and to End of Treatment (Weeks 23 through 24) between each active group and placebo.

- Difference in change in serum iron from Baseline to Week 13 and to End of Treatment (Weeks 23 through 24) between each active group and placebo.
- Difference in change in serum hepcidin from Baseline to Week 13 and to End of Treatment (Week 24) between each active group and placebo.
- Difference in percent change in serum NT-pro-BNP from Baseline to Week 13 and to End of Treatment (Weeks 23 through 24) between each active group and placebo in patients with baseline NT-pro-BNP > 250 pg/mL.
- Difference in change in hemoglobin from Baseline (average of the two most recent hemoglobin values prior to randomization and Day 1) to Week 13 and to End of Treatment (Weeks 23 through 24) between each active group and placebo in patients with baseline hemoglobin < 11 g/dL.
- Difference in change in serum albumin from Baseline (average of the two most recent serum albumin values prior to randomization and Day 1) to Week 13 and to End of Treatment (Weeks 23 through 24) between each active group and placebo in patients with baseline albumin < 4.0 g/dL.

### 3.2 Study Schematic

**Figure 5 Study Flow**

Ziltivekimab Dose Level 1, 2 or 3 (N=180); N=60 in each level															
		Placebo (N=60)													
Visit Number	Screening		Treatment Period											Safety F/U	
	-2	-1	1	2	3	4	5	6	7	8	9	10	11/ET	12	13/ET
Visit Day Window	-14	-7	1	8	22	29-35	43-49	57-63	85-91	113-119	141-147	155-161	162-168	190-196	218-224
Visit Window		±2	1	±2	±2										
Visit Week	-2	-1	1	2	4	5	7	9	13	17	21	23	24/ET	28	32/ET

### 3.3 Blinding and Randomization

#### 3.3.1 Randomization

Treatments will be assigned to randomized patients via an interactive web-response system (IWRS). Patients (N=240) will be randomized in 1:1:1:1 ratio to Ziltivekimab Dose #1 (7.5 mg), Ziltivekimab Dose #2 (15 mg), Ziltivekimab Dose #3 (30 mg) or matching Placebo, as they meet all entry criteria. Patients will be stratified by baseline hemoglobin ( $\geq 11$  or  $< 11$  g/dL) and CKD stage (3, 4 or 5). Note that CKD stage is stratified into two categories: (1) stage 3 and (2) stages 4 or 5.

#### 3.3.2 Blinding

This study is double-blind. The patients, investigators, site personnel, site monitors and Sponsor and the Contract Research Organization (CRO) clinical operational personnel will be blinded to the treatment assignment (see [Section 12.2](#) for details). Ziltivekimab and matching placebo will be provided as a liquid for subcutaneous injection.

The randomization list will be generated by a CRO statistician not otherwise involved in the study.

#### 3.3.3 Unblinding

In case of a medical emergency or medical situation in which the treatment assignment is necessary for proper patient management, the Investigator may obtain the treatment

assignment from the IWRS. The Investigator should make every reasonable attempt to contact the Medical Monitor before unblinding a patient. In all cases, the Investigator must submit a written report, including all pertinent details, to the Medical Monitor within 24 hours of the unblinding.

### **3.4 Duration of the Study**

The study will consist of three periods: Screening, Treatment Period, and Safety Follow-Up Period. The total study duration for an individual patient will be approximately 8-9 months. The study period durations are as follows:

Screening Period: up to 2 weeks [Days -14 to -1]

- Starts with the first date that Initial Screening procedures were performed. The first procedure also defines the initial screening visit date

Treatment Assessment Period: 24 weeks [Week 1, Day 1 through Week 24, ]

- Starts with the first administration of study drug/randomization (Day 1)

Safety Follow-Up Period: 8 weeks [Weeks 25 through 32]

- Safety period starts 4-weeks after last treatment dose 6.

### **3.5 Discussion of Study Design, Including Choice of Control Arm**

The study is a randomized, double-blind, placebo-controlled trial. Randomization and double-blinding are being used to minimize bias. The treatment duration (Weeks 1 through 24) was chosen as the shortest duration needed to evaluate the pharmacodynamic effect of said doses on the proposed inflammatory, hematologic and cardiovascular endpoints. Sample size calculations were performed for several pharmacodynamics endpoints and these are presented in [Section 11.1](#).

#### ***3.5.1 Study Population and Control Arm***

As there are currently no drugs approved for the treatment of functional iron deficiency and reduction of hs-CRP, there are no options for an active comparator.

The study is being conducted in the target population because the pharmacodynamic endpoints (inflammation, functional iron deficiency, and increased cardiovascular risk) cannot be evaluated in healthy volunteers.

#### ***3.5.2 Rationale for Dosing and Length of Safety Evaluation***

Inhibition of free IL-6 greater than 90% is needed to achieve biologic effect, because growth factors and soluble cytokines in general are able to elicit signaling with receptor occupancies of less than 10%. A basic logarithmic dose escalation scheme was used after modeling of

IL-6 binding and the PK-PD (hs-CRP) relationship from the concluded Phase 1 trial in RA patients (Study D4430C00001). Based on the clearance of Ziltivekimab (dictated by the “YTE” Fc mutation), the duration of safety monitoring and follow-up for PK, IL-6, and antibody testing to 32 weeks is planned.

### 3.5.3 *Rationale for the Efficacy Endpoints*

The inflammatory pharmacodynamic endpoint of hs-CRP was chosen as the primary endpoint because it is a direct measure of IL-6 function (specifically hs-CRP genes are induced by IL-6). The inflammatory biomarker hs-CRP has been shown to be a strong component in the prediction of cardiovascular risk to an extent approximately equivalent to total and high-density cholesterol (HDL) levels. Further data support that hs-CRP levels while on statin therapy are a large predictor of cardiovascular risk to a similar extent to those seen with LDL (Ridker 2016). However, CRP has a short circulating half-life of approximately 19 hours in which the plasma concentration is largely impacted by the rate of production through the biochemical pathway. Thus, CRP has not previously been considered an adequate target for intervention.

The biochemical pathway of CRP production is downstream regulated by IL-6 expression which is itself regulated by the downstream expression of IL-1, specifically the inhibition of the IL-1 $\beta$ -producing NOD-like receptor family pyrin domain containing 3 inflammasome. Thus, hs-CRP levels can be considered downstream surrogate biomarkers of both IL-6 and IL-1 expression when evaluating compounds which regulate their specific respective actions. Inhibition of IL-6 or IL-1 expression for the ultimate outcome of a reduction in circulating hs-CRP levels has been undertaken in several recent clinical studies (Ridker 2016).

The secondary endpoints include evaluations of fibrinogen and serum amyloid A (SAA). Fibrinogen is an acute phase reactant and a mediator of coagulation and therefore a marker of cardiovascular risk and a predictor of future cardiovascular risk (Ridker 2012). The difference in percent change in fibrinogen will be evaluated from Baseline to Week 13 between each active group and placebo. SAA is another acute phase reactant that was selected as an additional secondary endpoint because it is persistently elevated in chronic inflammatory conditions and elevated levels predict cardiovascular risk in humans (Shridas 2019). The difference in change in SAA will be evaluated from Baseline to Week 13 between each active group and placebo.

The exploratory endpoints include evaluations of NT-pro-BNP, ST2, albumin and hemoglobin. Serum NT-pro-BNP is a marker of cardiovascular risk and a predictor of future cardiovascular risk. Percent change in serum NT-pro-BNP will be evaluated from Baseline to Week 13 and to End of Treatment between each active group and placebo. Suppression of

tumorigenecity 2 (ST2) is a prognostic marker for heart failure with preserved and reduced ejection fraction. ST2 is a member of the interleukin 1 receptor family, also known as interleukin 1 receptor-like 1 (IL1RL-1). High circulating level of ST2 is associated to increased cardiovascular disease mortality and markers of metabolic dysfunction in subjects with atherosclerotic disease.

Serum albumin was selected as an additional exploratory endpoint because it is also closely negatively correlated with inflammation in the CKD population and is therefore also being analyzed as a marker of inflammation. Changes in serum albumin will be evaluated from Baseline to Week 13 and to End of Treatment between each active group and placebo. Hemoglobin was selected as an exploratory endpoint because of its sensitivity to IL-6. Changes in hemoglobin will be evaluated from Baseline to Week 13 and to End of Treatment between each active group and placebo.

In the inflammatory state, through the direct action of IL-6 there is overproduction of “the master iron regulator” hepcidin, a protein which prohibits cellular iron transport via degradation of ferroportin, the only known iron export channel in humans. This elicits a functional iron blockade that leads to anemia. Changes in serum hepcidin will be evaluated from Baseline to Week 13 and to End of Treatment between each active group and placebo.

Additional hematologic pharmacodynamic endpoints chosen include TSAT, CHr, TIBC, iron, and ferritin. These endpoints are intended to evaluate the effects of reducing inflammation on functional iron deficiency anemia. It is hypothesized that CHr will increase as iron is released from tissue stores. TSAT is also expected to increase over time as more iron is mobilized, until iron is utilized for erythropoiesis (reflected in rising hemoglobin).

Supportive pharmacodynamic endpoints include LDL-C, triglycerides, ApoB, ApoB/A1, and Lp(a). Biomarkers for CKD will be evaluated including cystatin C, creatinine, and UACR.

Finally, inflammation is known to affect systemic symptoms, notably fatigue and skeletal muscle strength; assessments will be made for selected items from the PROMIS Fatigue and 13a short form, Optum SF-36 v2® Health Survey, Corvidia ePRO, PGIS, PGIC, and EQ-5D-5L.

### **3.5.4            *Rationale for the Dose Regimens***

The main goal of Ziltivekimab dosing in the planned Phase 1/2 CKD patient study is to attain and maintain serum Ziltivekimab concentrations sufficient for  $\geq 90\%$  IL-6 binding over the treatment period, with a secondary goal of reducing hs-CRP to below 2 mg/L while keeping the highest planned dose more than 20-fold below the no adverse effect level (NOAEL) observed in primates.

### 3.5.4.1 Pharmacokinetic modeling

To date, the Ziltivekimab clinical program is comprised of 2 studies, both of which are placebo-controlled ascending dose studies. In the first of these studies (Study COR-001-01), patients with ESRD were administered intravenous (IV) infusions of study drug every 2 weeks for a total of 6 doses. Ten patients per cohort were randomized in a 1:4 ratio to placebo or Ziltivekimab (2, 6, and 20 mg).

In the second study (Study COR-001-SC1), patients with CKD were administered single subcutaneous (SC) doses of study drug. Four patients per cohort were randomized in a 1:3 ratio to placebo or Ziltivekimab (5, 15, and 50 mg).

The PK parameters are generally consistent with those expected for a monoclonal antibody. Absolute bioavailability (F) of SC administered Ziltivekimab is 69%, and the mean time of occurrence for peak serum Ziltivekimab concentrations ( $t_{max}$ ) after SC dosing ranged from 8 to 15 days, with an absorption half-life of 3 days. Terminal elimination half-lives ( $t_{1/2,z}$ ) differed between the ESRD patients (mean  $t_{1/2,z}$  ranging from 38 to 44 days) and CKD patients (mean  $t_{1/2,z}$  ranging from 48 to 56 days). While these results suggest that the rate of Ziltivekimab elimination may increase with decreasing renal function, a prior observation in rheumatoid arthritis patients that Ziltivekimab clearance is much slower than the glomerular filtration rate implies that the apparent elimination rate difference is not due to renal function *per se*, but more likely other physiological changes that accompany decreased renal function.

### 3.5.4.2 Correspondence of proposed doses to those used in prior clinical studies

Based on the clinical PK for Ziltivekimab described above, especially the F of 69.3% for SC dosing, the correspondence of proposed SC doses can be derived. [Table 1](#) provides a summary of the SC doses that would correspond to the Ziltivekimab doses used in prior studies. From this perspective, the proposed 7.5 and 15 mg q4w x 6 regimens are well within the range of exposures considered safe in the prior clinical study, and the proposed 30 mg q4w x 6 regimen is less than the exposure associated with adverse changes in laboratory parameters in the prior clinical study.

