Serious adverse events (SAEs) occurred at a higher rate in the 6 and 20 mg dose groups than in the placebo and 2 mg groups. The 6 mg group had the greatest incidence of SAEs (7 patients reporting a total 14 SAEs), and all 4 of the congestive cardiac failure events in the 6 mg group were considered serious. None of the SAEs in any group were assessed as treatment related. There were 4 patients who had SAEs with a fatal outcome; sepsis (Patient [REDACTED]) and sudden cardiac death (Patient [REDACTED]) in the 6 mg group and sepsis ([REDACTED]) and cardiac arrest ([REDACTED]) in the 20 mg group. None of the deaths were attributed to study drug; more information on the Safety results from study COR-001-01 can be found in the Investigator Brochure.

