## **2 STUDY GOAL AND OBJECTIVES**

Patients with NDD-CKD, who have evidence of systemic inflammation with increased cardiovascular risk, will be enrolled into this trial. The purpose of this trial is to determine a dose to select for a potential cardiovascular outcome trial with Ziltivekimab. The current trial will determine which dose of Ziltivekimab will have a significant reduction in hs-CRP with acceptable increases in LDL-C or triglycerides and without clinically meaningful reductions in neutrophils and platelet counts. Doses to be tested will be 7.5 mg, 15 mg and 30 mg subcutaneous monthly compared to placebo for six months.

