### **3.7 Benefit and Risk Assessment**

Despite the fact that the concept of inflammatory risk in renal patients has been in the public domain for decades, with an active basic research and clinical investigational community focused on its remediation, no therapy has been specifically designed or developed to address it. The advancement of an anti-inflammatory therapy for CKD patients should offer the benefit of myocardial protection and potential treatment of heart failure in this otherwise vulnerable population.

As for the risks associated with administration of Ziltivekimab, nonclinical toxicology studies established the NOAEL by the maximal dose administered (see the Ziltivekimab IB). Both in terms of local and systemic effects, Ziltivekimab was well tolerated, with no apparent adverse findings. Of note, the highest Ziltivekimab dose planned for study allows an over 20-fold margin to NOAEL in the non-clinical toxicology program.

Available data for anti-IL6R (tocilizumab) and anti-IL6 (siltuximab) therapies suggest neutralization of IL-6 have acceptable safety and tolerability profiles for the indications studied. Injection-related and life-threatening hypersensitivity reactions are rare with these agents. Anti-inflammatory therapies in general run the risk of inducing immune suppression and promoting the emergence of infections, sometimes serious in nature. Although anti-IL-6 therapies lower neutrophil counts and may induce frank neutropenia, their rates of infectious complications appear to be similar to other immune-modulatory biologic agents when accounting for patient-specific factors ([Sakai 2015](#), [Sanofi 2016](#)). Gastrointestinal perforation has been associated with anti-IL-6 therapy, however data suggests proper exclusion criteria may mitigate these risks ([Tanaka 2014](#)).

On balance then, the Sponsor proposes the potential risks to patients in this study are justifiable and the benefit-to-risk ratio positive. Patients will be consented as to the potential risks and will be required to sign an ICF documenting their understanding of these risks and willingness to participate in the study.

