#### **4.4 Anaphylaxis Study Stopping Rule**

If at any point during the study  $\geq 10\%$  of participants experience an anaphylaxis event, the anaphylaxis study stopping rule will be executed. The study stopping rule will halt any additional enrollment into the study for safety purposes. Additionally, all randomized participants currently receiving study drug will immediately discontinue further study drug administration. The remaining study procedures and visits may be performed if deemed necessary by the Sponsor.

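### Section 3.5.4.2 reassures on 15 mg, but on Table 1 that dose is 87% of the SC equivalent of the COR-001-01 cohort with the greatest SAE incidence

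*Protocol*

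**What the plan says.** Section 3.5.4.2 compares the planned subcutaneous (SC) doses with the intravenous (IV) doses of COR-001-01, the haemodialysis study, through Table 1. It concludes that "the proposed 7.5 and 15 mg q4w x 6 regimens are well within the range of exposures considered safe in the prior clinical study". For 30 mg it says only that exposure is below the level linked to adverse laboratory changes. It names no reference cohort for either statement.

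Section 1.4.3 gives the safety results of the same study. On serious events it says that they "occurred at a higher rate in the 6 and 20 mg dose groups than in the placebo and 2 mg groups". Incidence peaked at 6 mg (14 SAEs in 7 patients); of the cardiac events the section says that "all 4 of the congestive cardiac failure events in the 6 mg group were considered serious". Four patients had fatal SAEs: sepsis and sudden cardiac death at 6 mg, and sepsis and cardiac arrest at 20 mg. The section also says: "None of the SAEs in any group were assessed as treatment related". It attributes no death to study drug and reports no clear dose response for treatment-emergent events.

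Section 3.7 concludes that "the Sponsor proposes the potential risks to patients in this study are justifiable and the benefit-to-risk ratio positive". It cites primate margins and other anti-IL-6 agents, and does not mention the SAEs or deaths in COR-001-01.

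Section 2 says the trial is to find the dose that lowers hs-CRP significantly with "acceptable increases in LDL-C or triglycerides and without clinically meaningful reductions in neutrophils and platelet counts".

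**The concern.** Section 3.5.4.2 is where the protocol sets the planned doses against earlier human safety experience. Its conclusion on 15 mg cannot be squared with section 1.4.3 unless the range it has in mind extends to about the 6 mg cohort, where SAEs were most frequent. An ethics committee or investigator who reads only the dose rationale and the benefit-risk section would not learn of that pattern.

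The trial's purpose is to choose a dose for a cardiovascular outcome trial. Serious cardiac failure was prominent in the prior 6 mg cohort, yet heart failure is not an event of special interest in section 9.3. The dose-selection sentence in section 2 lists hs-CRP, lipids, neutrophils and platelets, but neither SAEs nor deaths.

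**Working it through.** **Inputs.** Bioavailability F = 69.3% (Table 1, footnote c). IV doses of 2, 6 and 20 mg every 2 weeks (Table 1). Planned SC doses of 7.5, 15 and 30 mg every 4 weeks, six times (section 3.5.4.4). Dose count in COR-001-01: 12 in Table 1, 6 in section 3.5.4.1.

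**Step 1: reproduce Table 1.** SC equivalent per 4 weeks = 2 × IV dose / 0.693.
- 2 mg: 4/0.693 = 5.77 mg
- 6 mg: 12/0.693 = 17.32 mg
- 20 mg: 40/0.693 = 57.72 mg

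These match the stated 5.8, 17.3 and 57.7 mg. This column does not depend on the dose count.

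**Step 2: planned doses against the cohorts.**

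| Planned SC dose | vs 2 mg (5.77) | vs 6 mg (17.32) | vs 20 mg (57.72) |
|---|---|---|---|
| 7.5 mg | 130% | 43% | 13% |
| 15 mg | 260% | 87% | 26% |
| 30 mg | 520% | 173% | 52% |

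The 15 mg dose lies just under the cohort with the greatest SAE incidence. The 30 mg dose lies between the two cohorts in which SAEs were raised and all four deaths occurred.

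**Step 3: sensitivity to F.** The ratio of 15 mg to the 6 mg cohort is 15F/12 = 1.25F. For an assumed F of 60% to 80% it runs from 75% to 100%.

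**Step 4: half-life.** Table 1 adjusts only for F. Section 3.5.4.1 gives mean half-lives of 48 to 56 days in CKD and 38 to 44 days in ESRD. If the volume of distribution is equal (an assumption), exposure per dose scales with half-life, by 48/44 = 1.09 to 56/38 = 1.47. In ESRD terms 15 mg then behaves like 16.4 to 22.1 mg, or 94% to 128% of 17.32 mg.

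**Step 5: dose count.** Cumulative SC equivalent = number of doses × IV dose / 0.693.

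| Cohort | 12 doses (Table 1) | 6 doses (3.5.4.1) |
|---|---|---|
| 2 mg | 34.6 mg | 17.3 mg |
| 6 mg | 103.9 mg | 51.9 mg |
| 20 mg | 346.3 mg | 173.2 mg |

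Planned cumulative doses are 45, 90 and 180 mg. With 12 doses, 90 mg is 90/103.9 = 87% of the 6 mg cohort. With 6 doses it is 90/51.9 = 173% of that cohort, and 180 mg is 180/173.2 = 104% of the 20 mg cohort. The protocol does not settle which count is right.

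**Step 6: how much the prior data can bear.** Section 3.5.4.1 gives ten patients per cohort at 1:4, which implies 8 active per cohort and 6 pooled placebo; actual arm sizes are not stated. On that assumption 7/8 had an SAE at 6 mg (exact 95% CI 47% to 99.7%), and deaths were 4/16 at 6 and 20 mg against 0/14 at 2 mg and placebo (Fisher two-sided p = 0.10). That grouping was formed after seeing where the deaths fell, and the protocol gives no SAE counts for the other arms.

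**The case against.** The strongest defence is that section 3.5.4.2 reports a judgement and section 1.4.3 supplies its basis: no SAE was judged treatment related, no death was attributed to drug, and treatment-emergent events showed no clear dose response. SAE incidence was greatest at 6 mg and not at 20 mg, which weakens a dose-related reading. If the range runs to the top of Table 1, 15 mg is only 26% of it. COR-001-01 enrolled genotype-selected haemodialysis patients with high IL-6 and high ESA needs. The single-dose SC study in CKD, a population nearer to this trial's, had one SAE (on placebo) and no deaths (section 1.4.2). Fuller results are said to be in the Investigator's Brochure, which is not at hand.

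Much of this stands: the data do not show that the drug caused harm. But section 3.5.4.2 does not argue from attribution. A range reaching the 20 mg cohort takes in both cohorts with raised SAE rates and all the deaths. Placebo and 2 mg patients came from the same haemodialysis study. Single doses in three active patients per cohort say little about six monthly doses.

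Two stronger readings are tempting, and the documents support neither.
- A reader might infer that only the 2 mg cohort was safe, so that every planned dose lies outside the safe range. Nothing in section 3.5.4.2 confines the range to that cohort, and 7.5 mg, though 130% of its equivalent, is only 43% of the 6 mg cohort's.
- A reader might infer that an SAE excess would play no part in choosing the dose. SAEs are a safety endpoint (section 3.1.2), and section 12.2 has the sponsor review all safety data at the 13-week analysis, including possible changes to the development programme. Sepsis is also partly covered: active infection is excluded (4.2), drug is withheld for serious infection (8.1), and serious infections are events of special interest (9.3).

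**Conclusion.** The point holds for 15 mg, and for the silence about SAEs and deaths at 30 mg. At 87% of the SC equivalent of the cohort with the greatest SAE incidence, 15 mg cannot be described as comfortably inside a safe range without explanation. At 173% of that cohort, 30 mg needs a comparison on more than laboratory values. The point is weak for 7.5 mg.

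The 87% rests on Table 1's 4-weekly column and F = 69.3%, and does not depend on the dose count. It also assumes that the prior study meant in section 3.5.4.2 is COR-001-01, the only one in Table 1. The disagreement between 12 and 6 doses is a separate factual error; if 6 is right, the cumulative comparison reverses for 15 mg against the 6 mg cohort and for 30 mg against the 20 mg cohort.

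This should be fixed as a matter of accurate dose justification. It is not evidence of toxicity and no reason to change the doses.

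**What to change.** - **Section 3.5.4.2:** name the reference cohort and the metric (SC-equivalent dose per 4 weeks), drop the claim that 15 mg sits comfortably inside a safe range, and state the SAE and death pattern by cohort with the attribution finding. Do the same for 30 mg. Carry the pattern into section 3.7.
- **Section 3.5.4.1 and Table 1:** confirm the COR-001-01 dose count and make them agree. If it is 6, the SC cumulative column becomes 17.3, 51.9 and 173.2 mg and the monthly column 2.9, 8.7 and 28.9 mg.
- **Sections 9.3 and 3.1.2:** add heart failure to the events of special interest, so that it is reported within 24 hours and summarised by arm.
- **Section 2:** add SAEs and deaths by arm to the dose-selection criteria, assessed at the 13-week review already planned in section 12.2.

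The cost is text changes and a little extra reporting. Doses, sample size and primary analysis are unchanged. Earlier unblinded by-arm review with a pause rule is a suggestion only: it needs extra resources and is a design choice that the sponsor may reasonably decline.
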